4.2 Exclusion criteria

Patients fulfilling **any** of the following criteria are NOT eligible for inclusion in this study. No additional exclusions may be applied by the investigator, in order to ensure that the study population will be representative of all eligible patients.

1. Use of other investigational drugs within 5 half-lives prior to first treatment.
2. History of hypersensitivity to vaccines, the study drug or to drugs of similar chemical classes (e.g. IgG₁-related biologic agents).
3. History of treatment of Graves' disease with radio-iodine ablation or thyroidectomy.
4. Current treatment with anti-thyroid drugs (methimazole or propylthiouracil) within one week of starting treatment. Discontinuation of ATD must not have been for the sole purpose of qualifying for this study; rather it should have been based on clinical considerations (e.g. lack of efficacy or safety/tolerability issues with ATD).
5. History of hyperthyroidism not caused by Graves' disease (e.g. toxic multinodular goiter, autonomous thyroid nodule, or acute inflammatory thyroiditis).
6. History or presence of thyroid storm (fever, profuse sweating, vomiting, diarrhea, delirium, severe weakness, seizures, markedly irregular heartbeat, yellow skin and eyes (jaundice), severe low blood pressure, and coma).
7. Previous treatment with a B cell-depleting biologic agent or any other immunomodulatory biologic agent (experimental or approved) within 5 half-lives prior to first treatment.
8. History of malignancy of any organ system (other than localized basal cell carcinoma of the skin), treated or untreated, within the past 5 years, regardless of whether there is evidence of local recurrence or metastases.
9. Significant illness which has not resolved within two weeks prior to initial dosing.
10. History of recurrent clinically significant infection or of recurrent bacterial infections with encapsulated organisms, including current, active or latent infection susceptible to reactivation.
11. History of primary or secondary immunodeficiency, including a positive HIV (ELISA and Western blot) test result at screening.
12. A positive Hepatitis B surface antigen or Hepatitis C test result at screening.
13. History or evidence of tuberculosis by either of the following tests at screening:
 - Positive PPD skin test (size of induration measured after 48-72 hours, and a positive result is defined as an induration of $\geq 5\text{mm}$ or according to local practice/guidelines) **OR**

Corporate Confidential
Information

- Positive QuantiFERON TB-Gold test

14. A negative Epstein Barr virus (EBV) test (as defined in the laboratory manual) at screening.

15. Any of the following abnormal laboratory values at screening (may be repeated one time for a single outlying value):

- Total white blood count (WBC) outside of the range $2.0-15.0 \times 10^9/L$
- Absolute neutrophil count $<1.5 \times 10^9/L$
- Lymphocyte count $<0.8 \times 10^9/L$
- Platelets $< 100 \times 10^9/L$
- Hemoglobin $< 9.0 \text{ g/dl}$

16. Severe liver disease or liver injury as indicated by abnormal liver function tests at screening:

- Any **single parameter** of ALT, AST, γ -GT, must not exceed $>5 \times$ the upper limit of normal (ULN);
- alkaline phosphatase (ALP) must not exceed $>5 \times$ the upper limit of normal (ULN);
- serum total bilirubin (TBL) must not exceed $>1.8 \times$ the upper limit of normal (ULN) except if the elevation is due to Gilbert's syndrome.

If necessary, laboratory testing may be repeated on one occasion (as soon as possible) prior to randomization, to rule out any laboratory error.

17. Inability or unwillingness to undergo repeated venipuncture (e.g., because of poor tolerability or lack of access to veins).

18. Donation or loss of 400mL or more of blood within eight (8) weeks prior to initial dosing or longer, if required by local regulation.

19. Plans for immunization with a live vaccine within a 2-month period before enrollment or during the study period.

20. History or evidence of drug or alcohol abuse within the 6 months prior to dosing, or evidence of such abuse as indicated by the laboratory assays conducted during screening.

21. Treatment with immunomodulatory drugs, such as cyclosporine A, methotrexate, and/or cyclophosphamide within 3 months from baseline. Glucocorticosteroid therapy with prednisolone up to 10 mg daily is permitted if patients are on stable dose for more than 3 months before enrollment in the study.

22. History or presence of coronary artery disease, ventricular or atrial arrhythmias (including atrial fibrillation) with the exception of sinus tachycardia controlled with beta-blockers.

23. Pregnant or breast-feeding women, where pregnancy is defined as the state of a female after conception and until the termination of gestation, confirmed by a positive hCG laboratory test.

24. Women of child-bearing potential, defined as all women physiologically capable of becoming pregnant, unless they are using highly effective methods of contraception during dosing and for 12 weeks after stopping medication. Highly effective contraception methods include:

- Total abstinence (when this is in line with the preferred and usual lifestyle of the subject. Periodic abstinence (i.e., calendar, ovulation, symptothermal, postovulation methods) and withdrawal are not acceptable methods of contraception)
- Female sterilization (have had surgical bilateral oophorectomy (with or without hysterectomy), total hysterectomy or tubal ligation at least six weeks before taking study treatment. In case of oophorectomy alone, only when the reproductive status of the woman has been confirmed by follow up hormone level assessment)
- Male sterilization (at least 6 m prior to screening). The vasectomized male partner should be the sole partner for that subject
- Use of oral, injected or implanted hormonal methods of contraception or placement of an intrauterine device (IUD) or intrauterine system (IUS) or other forms of hormonal contraception that have comparable efficacy (failure rate <1%), for example hormone vaginal ring or transdermal hormone contraception

In case of use of oral contraception women should have been stable on the same pill for a minimum of 3 months before taking study treatment.

25. Sexually active males must use a condom during intercourse while taking CFZ533 and for 12 weeks after stopping the investigational medication and should not father a child in this period. A condom is required to be used also by vasectomized men in order to prevent delivery of the drug via seminal fluid.

26. Treatment with amiodarone within 9 months of starting treatment in this study.

Note: In the case where a safety laboratory assessment at screening and initial baseline is outside of the range specified above, the assessment may be repeated once prior to randomization. If the repeat value remains outside of the specified ranges, the patient is excluded from the study.

No additional exclusions may be applied by the investigator, in order to ensure that the study population will be representative of all eligible patients.

5 Restrictions for study patients

During recruitment, screening/informed consent review, and baseline visit, the patients must be informed and reminded of the following restrictions:

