2.2 Secondary objective

Objective	Endpoint

To assess the safety and tolerability of CFZ533 (10 mg/kg IV for 12 weeks) up to 36 weeks	
Adverse events

[figure not shown]
Corporate Confidential Information

3 **Investigational plan**

3.1 **Study design**

This is a non-confirmatory, open-label, one treatment arm study in patients with GD.

A total of approximately 15 patients will be enrolled and treated with CFZ533 to ensure approximately 12 completers. For each patient, the study will consist of a screening epoch of up to 28 days, a baseline evaluation, a 12-week treatment epoch, 24-week follow up epoch after the last dosing of CFZ533 on Study Day 85, and a study completion evaluation on Study Day 253. Patients who discontinue the drug before having completed 4 weeks of treatment and 4 week efficacy and safety evaluations will be replaced with a newly enrolled patient. The study completion assessments (End of Study; EOS) should be completed in patients who discontinue the study. The study design is presented in [Figure 3-1](#).

Figure 3-1 Study design

Patients who meet the eligibility criteria at screening will be admitted to baseline evaluations. Baseline evaluations may be started from Day -7 to allow completion of assessments prior to the treatment on Study Day 1. All baseline safety evaluation results must be available prior to dosing and meeting the eligibility criteria. The baseline visit (Visit 99) can be skipped and the baseline assessments would be completed prior to the study treatment on Day 1 (Visit 101) if Day 1 is scheduled within 7 days of the screening visit (Visit 1).

Eligible patients will enter the study to receive treatment with CFZ533 at 10 mg/kg IV over approximately one hour on Study Day 1. Patients will be monitored closely for at least 2 hours, at the discretion of the Investigator, after the completion of IV administration of CFZ533 for vital signs and adverse events, including development of an injection reaction.

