3.6.2 Potential risks associated with CFZ533 administration and their mitigation

Currently, limited data exists regarding the use of agents that block the CD40/CD154 pathway. Preclinical and Phase 1 data for CFZ533 as well as data from compounds acting on the same pathway (i.e., CD40-CD154) have been taken into account to estimate the potential risks associated with CFZ533. The risks to patients in this trial will be minimized by adherence to the eligibility criteria, close clinical monitoring, avoidance of prohibited treatments and overall adherence to terms outlined in this protocol. The current IB (Section 6, Investigator Guidance) also provides detailed instructions regarding the risks and their mitigation.

Acute hypersensitivity

Hypersensitivity or infusion reactions can manifest with itching, flushing, headache, nausea/vomiting, hypotension, urticaria, bronchospasm, or angioedema.

In this study, CFZ533 will be administered as an intravenous infusion where such hypersensitivity reactions can still occur. Patients will be monitored for at least 2 hours after the completion of CFZ533 IV infusion at each visit.

Immunogenicity

Corporate Confidential Information

Extrapolation of immunogenicity risks from healthy subjects to Graves' disease patients is unknown and blood samples will be collected during this trial to assess the immunogenicity.

Infections

Subjects treated with CFZ533 may be at an increased risk of infection. CD40 ligation is linked to the functional activity of antigen presentation, as well as T-cell priming, B-cell differentiation, antibody production and immune memory.

Administration of CFZ533 is expected to result in general immunosuppression with a decreased capacity to mount a response to novel immunogens, including those of bacterial, viral, fungal and parasitic origin when full receptor occupancy has been achieved.

Although the ability to mount a primary immune response will be affected by CFZ533, the memory B-cell repertoire and immune recall response should remain intact and protective. In addition, subjects will have adequate preformed antibody to maintain protective humoral response for extended periods of time (months).

Corporate Confidential Information

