Although not expected in this clinical study, the investigator will monitor for signs, symptoms and laboratory results consistent with clinically significant inflammation as well as for changes in renal function and signs of acute kidney injury as per local practice.

Vaccination

Vaccination of patients during treatment with CFZ533 and prior to clearance of the antibody is likely to result in therapeutic failure (i.e., non-protective antibody titers) due to the pharmacologic activity of CFZ533. For patients participating in this study, all vaccinations should be up to date based on local guidelines. Administration of live attenuated agents will be prohibited in patients receiving CFZ533 treatment in this study.

There may be other unknown risks to CFZ533 which may be serious and unforeseen.

Blood samples will be collected frequently during the study either via venipuncture or cannula. Approximately 460 mL of blood is planned to be collected over the study duration (~36-week) from each patient. Additional samples for monitoring of any safety findings would be in addition to this. This is not considered to be a risk for this population.

4 Population

The study population will be comprised of male and female patients 18 to 65 years of age with Graves' disease hyperthyroidism.

To ensure 12 completers, a total of approximately 15 patients will be enrolled to participate in this study.

The investigator must ensure that all patients being considered for the study meet the following eligibility criteria. No additional criteria should be applied by the investigator, in order to ensure that the study population will be representative of all eligible patients.

Patient selection is to be established by checking through all inclusion/exclusion criteria at screening and/or baseline. A relevant record (e.g. checklist) of the eligibility criteria must be stored with the source documentation at the study site.

Deviation from **any** entry criterion excludes a patient from enrollment into the study.

Replacement patients will be enrolled to replace patients who discontinue the study for reasons other than safety before having completed 4 weeks of treatment and 4 week efficacy and safety evaluations.

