4.1 Inclusion criteria

Patients eligible for inclusion in this study have to fulfill **all** of the following criteria at screening:

1. Written informed consent must be obtained before any assessment is performed.
2. Male and female patients 18 to 65 years of age included.
 - Women of child-bearing potential must be willing to use the highly effective methods of contraception (definition in Exclusion criteria #24) during the study treatment epoch and for 12 weeks after the last study treatment.

3. Graves' hyperthyroidism ([Baskin et al 2002](#)) with the following labs measured at screening:
 - TSH<LLN and either FT3>ULN or FT4> ULN
4. Patients must weigh at least 40 kg to participate in the study
5. Able to communicate well with the investigator, to understand and comply with the requirements of the study.
6. Patients have received up to date required vaccinations based on local guidelines.

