5.2 Prohibited treatment

Use of the treatments displayed in the table below is NOT allowed after the start of study drug until the end of study evaluation.

Table 5-1 Prohibited treatment

Medication	Action to be taken
Iodine (radioactive or cold)	Withdrawal may be required on a case-by-case basis
Methimazole	
Propylthiouracil	
Amiodarone	
Live vaccinations	Withdrawal immediately

Patients may continue the medications that had been taken before enrolling in this study and may take medications that are permitted per protocol. Doses may be titrated if deemed necessary by their physicians.

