6.10 Concomitant treatment

Patients may be treated with any medications that are not listed as prohibited treatment, as standard of care for their medical conditions by their physicians. Use of beta-blockers for treating the symptoms of Graves' disease during participation in this study is permitted at the discretion of the treating physician. Medication, amount and frequency of use must be recorded.

The investigator should instruct the patient to notify the study site about any new medications he/she takes after the start of the study drug.

Administration of acetaminophen is acceptable at the discretion of treatment physicians, but must be documented.

Should a patient have an incidental and limited need for a medication to be taken within the restricted pre-dose timeframe (e.g. acetaminophen for a headache, antibiotic prophylaxis prior to dental surgery, etc.), the sponsor should be advised, as administration of any concomitant medication may require the patient to be replaced. Decisions regarding replacements will be discussed with the sponsor on a case-by-case basis.

All prescription medications, over-the-counter drugs and significant non-drug therapies (including physical therapy and blood transfusions) administered or taken within the timeframe defined in the entry criteria prior to the start of the study and during the study, must be recorded on the Concomitant medications/ Significant non-drug therapies section of the CRF.

Medication entries should be specific to trade name, the amount of single doses and units, the dosing frequency, route of administration, the start and discontinuation dates, and the medical reason for the therapy.

7 Discontinuation and study completion

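### Exclusion 19 names only plans for a live vaccine, so read literally it does not exclude a patient who received one in the 2 months before enrollment

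*Protocol*

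**What the plan says.** Exclusion 19 in Protocol section 4.2 reads "Plans for immunization with a live vaccine within a 2-month period before enrollment or during the study period". The key exclusion criteria in the synopsis repeat it word for word. Plans is the only noun, and it governs both the 2-month look-back and the study period.

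Other text on vaccines or prior medication:

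- Inclusion 6 (section 4.1): "Patients have received up to date required vaccinations based on local guidelines". It sets no interval before entry and does not mention live vaccines.
- Exclusion 2 (section 4.2) concerns hypersensitivity to vaccines, not recent vaccination.
- Section 3.6.2, Vaccination: "Administration of live attenuated agents will be prohibited in patients receiving CFZ533 treatment in this study".
- Section 5.2: the treatments in Table 5-1, which include live vaccinations, are "NOT allowed after the start of study drug until the end of study evaluation". The listed action for a live vaccination is immediate withdrawal.
- Section 6.10: medications "administered or taken within the timeframe defined in the entry criteria prior to the start of the study and during the study" must be recorded in the CRF.

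The SAP has no eligibility rule on this point.

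**The concern.** A look-back before enrollment serves mainly to catch something that has already happened. A plan concerns the future, so the noun does not fit most of the window. Section 4 asks sites to keep an eligibility record such as a checklist. A checklist that copies exclusion 19 asks about plans, and a recently vaccinated patient with nothing further scheduled can truthfully answer no.

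What is at stake is patient safety at entry. Section 3.6.2 (Infections) expects CFZ533 to bring general immunosuppression, with a reduced "capacity to mount a response to novel immunogens, including those of bacterial, viral, fungal and parasitic origin when full receptor occupancy has been achieved". That state comes after dosing, so a live vaccine given days before Day 1 could still be recent when it begins. Inclusion 6 offers a practical route: a patient brought up to date in order to qualify could be vaccinated shortly before screening. This assumes that a locally required vaccine is live, which the documents do not say.

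**Working it through.** The plan states no figure to reproduce. The check has three parts.

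**1. How much of the window is past when eligibility is checked**

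Inputs:

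- Look-back: 2 months (exclusion 19). Two consecutive calendar months are 59 to 62 days.
- Longest screening: 28 days. Section 3.1 says "the study will consist of a screening epoch of up to 28 days".
- Enrollment is not tied to a visit in exclusion 19, so both readings are taken.

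Formula: past share = (window − days from screening to enrollment) / window.

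| Meaning of enrollment | Window (days) | Days from screening to enrollment | Past days | Past share |
|---|---|---|---|---|
| Screening | 59 to 62 | 0 | all | 100% |
| Day 1, screening at Day −28 | 59 | 28 | 59 − 28 = 31 | 31/59 = 52.5% |
| Day 1, screening at Day −28 | 62 | 28 | 62 − 28 = 34 | 34/62 = 54.8% |

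A shorter screening raises the last two shares. So at least 53% of the window (rounded), and up to all of it, lies before screening. Only a question about receipt can cover those days.

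**2. How the other look-backs in section 4.2 are worded**

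Windows for an illness, event or treatment appear in exclusions 1, 4, 7, 8, 9, 18, 19, 20, 21 and 26. Exclusion 21 has two (immunomodulatory drugs before baseline, stable prednisolone before enrollment). That makes 10 exclusions and 9 × 1 + 2 = 11 windows. The contraception definitions in exclusion 24 are not counted.

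Ten of the 11 name something past or current, for example blood donation or loss in no. 18 and amiodarone treatment in no. 26. One names plans: no. 19.

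**3. Whether another rule closes the gap**

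| Rule | Why it does not cover a live vaccine already received |
|---|---|
| Inclusion 6 | Requires vaccination and sets no minimum interval |
| Exclusion 2 | Hypersensitivity only |
| Section 3.6.2, Vaccination | Applies to patients receiving CFZ533 |
| Section 5.2, Table 5-1 | Applies after the start of study drug |
| Section 6.10 | Governs recording, not eligibility |

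None of them excludes a patient for a live vaccine received before enrollment.

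**The case against.** The strongest reply is that the intent is obvious. A 2-month look-back has little purpose unless it covers vaccines already given, so most sites would ask about receipt. Doing so applies the criterion as meant and does not breach the ban on extra exclusions. This stands, and it is the main reason the point is minor. It does not repair the text, since a site that follows the words has no rule to apply.

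The route through inclusion 6 is also narrower than it may seem. Inclusion criteria must be met at screening, and a patient then scheduled for a live vaccine has a plan, which exclusion 19 catches as written. The gap is therefore mainly a vaccine received before screening. It can still fall days before Day 1, because section 3.1 allows the first dose within 7 days of screening.

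The documents tie no stated harm to the gap. The vaccination risk in section 3.6.2 is that "Vaccination of patients during treatment with CFZ533 and prior to clearance of the antibody is likely to result in therapeutic failure", which concerns vaccination during treatment. This stands: the safety argument is an inference from the expected immunosuppression.

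Exclusion 9 (significant unresolved illness) and exclusion 10 (active or latent infection) would catch a clinically apparent vaccine-derived infection. They give partial cover and do not ask about vaccination. The Investigator's Brochure, which section 3.6.2 cites for risk mitigation, may give guidance but is not among the documents.

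Finally, the window shares and the 1-in-11 count describe the wording, not the number of patients or the risk. That is correct.

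**Conclusion.** The concern holds. As written, exclusion 19 does not exclude a patient who received a live vaccine in the 2 months before enrollment, and no other criterion does. For 53% to 100% of its own look-back, the criterion names something that cannot apply.

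The weight is small. The intended meaning is probably clear to many sites, the number affected among about 15 patients cannot be derived, and nothing in the estimation or testing depends on it. It merits correction because it is an operative safety rule whose literal reading defeats the look-back that the sponsor chose.

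The conclusion rests on the literal reading and on the visible text. The shares rest on calendar months of 59 to 62 days and on enrollment meaning either screening or Day 1.

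**What to change.** Replace exclusion 19 and the synopsis line with: *Receipt of a live vaccine in the 2 months before enrollment, or a plan to receive one during the study, including between screening and first dose.* The 2-month length and the enrollment anchor stay as they are. If enrollment means screening, an unplanned live vaccine between screening and Day 1 would still not be named.

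The cost is one line in section 4.2 and one in the synopsis, which can wait for the next amendment. Some recently vaccinated patients might enter later or be excluded, including any who need a live vaccine to meet inclusion 6, because a wait of 59 to 62 days does not fit in a 28-day screening epoch. A patient put on anti-thyroid drugs while waiting could be lost, since exclusion 4 does not allow those drugs to be stopped only in order to qualify.
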